### **Serious Infections**

Monitor patients on idelalisib for signs and symptoms of infection, and interrupt idelalisib for Grade 3 or higher infection.

Serious and fatal infections have occurred with idelalisib, including opportunistic infections such as *Pneumocystis jirovecii* pneumonia (PJP) and cytomegalovirus (CMV). These infections have most frequently occurred the first 6 months of idelalisib treatment.

All subjects will receive trimethoprim-sulfamethoxazole or other established for PJP throughout the treatment with idelalisib. Prophylaxis should continue until the CD4+ T-cell count is documented  $>200$  cells/ $\mu$ l following the end of treatment. Interrupt idelalisib in patients with suspected PJP infection of any grade, and permanently discontinue idelalisib if PJP infection of any grade is confirmed.

Subjects have to be monitored each 15 days starting from day 1 for CMV throughout the course of idelalisib treatment (CMV PCR or antigen test). If unequivocal clinical or laboratory evidence of CMV infection is present, the subject has to discontinue idelalisib until the viremia has resolved and undergo effective antiviral treatment according to established clinical guidelines.

If idelalisib is subsequently resumed, patients should be monitored by PCR or antigen test for CMV reactivation at least monthly.

Patients should be monitored for respiratory signs and symptoms throughout treatment. Patients should be advised to report new respiratory symptoms promptly.

### **Hepatotoxicity**

Withhold idelalisib in the event of a Grade 3 or 4 aminotransferase elevation (ALT/AST  $\geq 5$  ULN). Once values have returned to Grade 1 or below (ALT/AST  $\leq 3$  ULN), resume idelalisib at 100 mg twice daily.

If the event dose not recur, the dose can be escalated to 150 mg twice daily after consulting with the Medical Monitor. If the event recurs, withhold until return to Grade 1 or below, after which re-initiation may be considered after consulting with the Medical Monitor.

Avoid concurrent use of idelalisib with other drugs that may cause liver toxicity.

### **Severe Diarrhea/Colitis**

Withhold idelalisib for diarrhea of Grade 3 or 4. Once diarrhea has returned to Grade 1 or below, resume idelalisib at 100 mg daily. If the diarrhea does not recur, the dose can be re-escalated to 150 mg twice daily after consulting with the Medical Monitor.

Avoid concurrent use of idelalisib and other drugs that cause diarrhea.

### **Intestinal Perforation**

Fatal and serious intestinal perforation occurred in idelalisib-treated patients. At the time of perforation, some patients had moderate to severe diarrhea. Advise patients to promptly report any new or worsening abdominal pain, chills, fever, nausea, or vomiting. Discontinue idelalisib permanently in patients who experience intestinal perforation.

### **Pneumonitis**

Fatal and serious pneumonitis occurred in patients treated with idelalisib. Clinical manifestations included interstitial infiltrates and organizing pneumonia. Time to onset of pneumonitis ranges from  $<1$  to 15 months. Monitor patients on idelalisib for pulmonary symptoms. In patients taking idelalisib who present with pulmonary symptoms such as cough, dyspnea, hypoxia, interstitial infiltrates on a radiologic exam, or a decline by more than 5% in oxygen saturation, withhold

idelalisib until the etiology has been determined. If symptomatic pneumonitis or organizing pneumonia is diagnosed, initiate appropriate treatment with corticosteroids.

Once pneumonitis has resolved and if re-treatment is deemed eligible for Medical Monitor, resumption of treatment at 100 mg twice daily can be considered.

### **Severe cutaneous reactions**

Fatal cases of Stevens-Johnson syndrome (SJS) and toxic epidermal necrolysis (TEN) have occurred in patients treated with idelalisib. If SJS or TEN is suspected, interrupt idelalisib until the etiology of the reaction has been determined. If SJS or TEN is confirmed, permanently discontinue idelalisib.

Other severe or life-threatening (Grade  $\geq 3$ ) cutaneous reactions, including dermatitis exfoliative, rash, rash erythematous, rash generalized, rash macular, rash maculo-papular, rash papular, rash pruritic, exfoliative rash, and skin disorder, have been reported in idelalisib-treated patients. Monitor patients for the development of severe cutaneous reactions and withhold idelalisib. Once cutaneous reaction has returned to Grade 1 or below, resume idelalisib at 100 mg twice daily. If reaction do not recur, the dose can be re-escalated to 150 mg twice daily after consulting with the Medical Monitor.

### **Anaphylaxis**

Serious allergic reactions, including anaphylaxis, have been reported in patients on idelalisib. In patients who develop serious allergic reactions, discontinue idelalisib permanently and institute appropriate supportive measures.

For more details, please refer to *Appendix E* or the IB.

### **Obinutuzumab**

There will be no obinutuzumab dose modification in this study. Consider treatment interruption if patients experience an infection, Grade 3 or 4 cytopenia, or a  $\geq$  Grade 2 non-hematologic toxicity. Any NCI CTCAE (v. 5.0) toxicity Grade  $\geq 3$  in severity that is deemed related to obinutuzumab treatment will require interruption of study treatment until resolution to Grade  $\leq 2$  or  $\geq 80\%$  of baseline, whichever is lower.

Resumption of obinutuzumab treatment may be considered in patients with resolution of toxicities to Grade  $\leq 1$  within 2 weeks at the discretion of the investigator, after consultation with the Medical Monitor. Failure of such toxicities to resolve after 2-week delay in study treatment will require permanent discontinuation of obinutuzumab.

Continuation of study treatment following dose delays beyond 2 weeks will require consultation with and approval of the Medical Monitor based on an assessment of the benefit-risk analysis of continuing to delay study treatment.

Patients in whom toxicities have not resolved (i.e., to Grade  $\leq 1$  or  $\geq 80\%$  of baseline) may have their study treatment delayed by up to 2 weeks. If all study drug-related toxicities have resolved to Grade  $\leq 1$  or  $\geq 80\%$  of baseline, the patient may resume idelalisib and obinutuzumab dosing on the regular every-28-day schedule.

Patients who do not fulfill the criteria for dosing after the additional 2 weeks have elapsed may be discontinued from study treatment and be followed for safety outcomes. Exceptions on the basis of ongoing clinical benefit may be allowed following a careful assessment and discussion of risk versus benefit with the patient by the investigator and approval from the Medical Monitor. In addition, delay of therapy because of toxicities not attributed to study drug may not require discontinuation and will be discussed with the Medical Monitor.

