## Dose Modifications for Toxicities Due to Zydelig

Pneumonitis	Any symptomatic pneumonitis		
	Discontinue Zydelig in patients with any severity of symptomatic pneumonitis		
ALT/AST	>3-5 × ULN	>5-20 × ULN	>20 × ULN
	Maintain Zydelig dose. Monitor at least weekly until <1 × ULN.	Withhold Zydelig. Monitor at least weekly until ALT/AST are <1 × ULN, then may resume Zydelig at 100 mg BID.	Discontinue Zydelig permanently.
Bilirubin	>1.5-3 × ULN	>3-10 × ULN	>10 × ULN
	Maintain Zydelig dose. Monitor at least weekly until <1 × ULN.	Withhold Zydelig. Monitor at least weekly until bilirubin is <1 × ULN, then may resume Zydelig at 100 mg BID.	Discontinue Zydelig permanently.
Diarrhea*	Moderate diarrhea	Severe diarrhea or hospitalization	Life-threatening diarrhea
	Maintain Zydelig dose. Monitor at least weekly until resolved.	Withhold Zydelig. Monitor at least weekly until resolved, then may resume Zydelig at 100 mg BID.	Discontinue Zydelig permanently.
Neutropenia	ANC 1.0 to <1.5 ·10^9/L	ANC 0.5 to <1.0 ·10^9/L	ANC <0.5 ·10^9/L
	Maintain Zydelig dose.	Maintain Zydelig dose. Monitor ANC at least weekly.	Interrupt Zydelig. Monitor ANC at least weekly until ANC ≥0.5 Gi/L, then may resume Zydelig at 100 mg BID.
Thrombocytopenia	Platelets 50 to <75 ·10^9/L	Platelets 25 to <50 ·10^9/L	Platelets <25 ·10^9/L
	Maintain Zydelig dose.	Maintain Zydelig dose. Monitor platelet counts at least weekly.	Interrupt Zydelig. Monitor platelet count at least weekly. May resume Zydelig at 100 mg BID when platelets ≥25 Gi/L.
Infections	Grade 3 or higher sepsis or pneumonia		
	Interrupt Zydelig until infection has resolved.		
	Evidence of CMV infection or viremia		
	Interrupt Zydelig in patients with evidence of active CMV infection of any grade or viremia (positive PCR or antigen test) until the viremia has resolved. If Zydelig is resumed, monitor patients by PCR or antigen test for CMV reactivation at least monthly.		
	Evidence of PJP infection		
	Interrupt Zydelig in patients with suspected PJP infection of any grade. Permanently discontinue Zydelig if PJP infection is confirmed.		

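### Section 13.12 gives conflicting idelalisib restart and stopping rules for raised ALT/AST, diarrhea and pneumonitis, and its two-drug restart sentence does not settle them

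*Combined protocol and SAP*

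**What the plan says.** Section 13.12 opens its idelalisib part by sending the reader to a table and to the paragraphs below it, without ranking them.

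- **ALT/AST.** For >5–20 × ULN the table says "Withhold Zydelig. Monitor at least weekly until ALT/AST are <1 × ULN, then may resume Zydelig at 100 mg BID"; above 20 × ULN it stops idelalisib permanently. The Hepatotoxicity paragraph withholds for Grade 3 or 4 (≥5 ULN), restarts at 100 mg twice daily once values are ≤3 ULN, and allows later escalation to 150 mg twice daily after consulting the Medical Monitor.
- **Diarrhea.** For severe diarrhea or hospitalization the table says "Withhold Zydelig. Monitor at least weekly until resolved, then may resume Zydelig at 100 mg BID"; life-threatening diarrhea means a permanent stop. The Severe Diarrhea/Colitis paragraph withholds for Grade 3 or 4, restarts at Grade 1 or below with 100 mg daily, and allows re-escalation.
- **Pneumonitis.** The table discontinues idelalisib for symptomatic pneumonitis of any severity. The Pneumonitis paragraph lets resumption at 100 mg twice daily be considered after resolution, if the Medical Monitor finds the patient eligible.

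Under Obinutuzumab, two sentences define resolution as Grade ≤1 or ≥80% of baseline. The delay sentence begins "Patients in whom toxicities have not resolved (i.e., to Grade". The restart sentence begins "If all study drug-related toxicities have resolved to Grade" and ends "of baseline, the patient may resume idelalisib and obinutuzumab dosing on the regular every-28-day schedule". It states no idelalisib dose and does not refer to the idelalisib rules.

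**The concern.** A multicenter trial needs one answer to whether, when and at what dose a patient goes back on a drug after a serious reaction. Section 13.11 warns of fatal or serious hepatotoxicity, diarrhea or colitis, and pneumonitis with idelalisib. For these same three toxicities, 13.12 gives two answers. Where one rule stops the drug permanently and the other allows a restart, a site can re-expose a patient and still be within the protocol.

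There is also a reporting consequence. Section 17.3 plans separate summaries of adverse events leading to interruption or dose modification and of those leading to discontinuation. With 12 sites free to follow either rule, these counts would partly reflect which text a site read.

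The Obinutuzumab restart sentence could have resolved this, because it names both drugs and covers all study drug-related toxicities. Instead it adds a third criterion, whose percentage part has no direction.

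**Working it through.** The plan gives no figure to reproduce here, so the check sets the rules side by side and applies them to cases.

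**1. Idelalisib rules compared**

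| Event | Table | Paragraph |
|---|---|---|
| ALT/AST restart | <1 × ULN, 100 mg BID | ≤3 ULN, 100 mg twice daily |
| ALT/AST >20 × ULN | permanent stop | withheld as Grade 3 or 4, then restart |
| Severe diarrhea | when resolved, 100 mg BID | at Grade ≤1, 100 mg daily |
| Life-threatening diarrhea | permanent stop | withheld as Grade 4, then restart |
| Symptomatic pneumonitis | discontinue | restart may be considered |
| Return to 150 mg BID | not mentioned | allowed for liver, diarrhea and skin |

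Life-threatening is equated with Grade 4, as in the severity scales of 16.2 and 17.3.

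**2. ALT/AST cases (assumed values, × ULN)**

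- Peak 10, now 2.5. Table: 2.5 is not <1, so keep withholding. Paragraph: 2.5 ≤ 3, so restart at 100 mg twice daily.
- Peak 25, now 0.9. Table: 25 > 20, so permanent stop. Paragraph: 0.9 ≤ 3, so restart.
- Peak 10, now 6: both withhold. Peak 10, now 0.9: both restart at 100 mg twice daily.

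So the rules part for peaks in the >5–20 band with current values from 1 to 3, and for every peak above 20 once values are ≤3.

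**3. Daily dose.** Full dose 2 × 150 = 300 mg. Table restart 2 × 100 = 200 mg. Diarrhea paragraph 1 × 100 = 100 mg, half the table's dose.

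**4. The 80% test.** A value v passes if v ≥ 0.8 × baseline b.

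- For a falling value the test works. With an assumed neutrophil baseline of 4.0, the level is 0.8 × 4.0 = 3.2; a count of 0.4 fails and 3.2 passes.
- For a rising value, any v > b passes, because v/b > 1 > 0.8. At the highest ALT/AST allowed by 11.2 without liver involvement (2.5 × ULN), the level is 0.8 × 2.5 = 2.0 × ULN. Values of 3, 5 and 20 × ULN are 3/2.5 = 120%, 5/2.5 = 200% and 20/2.5 = 800% of baseline, and all pass.
- For bilirubin at the 1.5 mg/dL entry limit, outside the 11.2 exceptions, the level is 0.8 × 1.5 = 1.2 mg/dL. The laboratory ULN is not given; the table's withhold band (>3 × ULN) passes for any ULN of at least 1.2/3 = 0.4 mg/dL. The table itself requires "Withhold Zydelig. Monitor at least weekly until bilirubin is <1 × ULN, then may resume Zydelig at 100 mg BID".
- The reference is the patient's own baseline, not the ULN. With an assumed baseline of 8 × ULN (liver involvement), a value of 6 × ULN is 6/8 = 75% and fails.

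**5. Cytopenias differ in the other direction.** The table says "Interrupt Zydelig. Monitor ANC at least weekly until ANC ≥0.5 Gi/L, then may resume Zydelig at 100 mg BID" and "May resume Zydelig at 100 mg BID when platelets ≥25 Gi/L". At the entry limits in 11.1 (disease-related exceptions aside), the 80% levels are 0.8 × 1.5 = 1.2 for neutrophils and 0.8 × 75 = 60 for platelets. The table limits are under one third of any such baseline (0.5/1.5 = 25/75 = 1/3, and eligible baselines lie above 1.5 and 75).

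**6. How many patients might reach these rules.** Assuming the idelalisib rates quoted in 7.2 and 13.11 apply to 43 patients:

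- Liver: 43 × 0.13 = 5.6; 43 × 0.16 = 6.9; 43 × 0.18 = 7.7.
- Diarrhea or colitis: 43 × 0.13 = 5.6; 43 × 0.14 = 6.0; 43 × 0.20 = 8.6.
- Pneumonitis: 43 × 0.04 = 1.7.

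The groups overlap. They count patients with the toxicity, not patients for whom the rules would diverge.

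**The case against.** The strongest objection concerns the 80% test. A reader might infer that the protocol permits restart at peak transaminases. The documents do not support that as an intended rule. The sentence requires toxicities to have resolved, its wording is permissive, and it sits under the Obinutuzumab heading. The separate obinutuzumab resumption rule needs Grade ≤1 and Medical Monitor consultation. The mandatory-interruption sentence keeps Grade ≤2 in force by taking the lower of its two criteria, so no gap is claimed there. What stands is narrower: the percentage arm cannot tell recovered from unrecovered liver values.

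A reader might also infer that idelalisib restarts at 150 mg BID. That too goes beyond the text. Section 13.11 directs sites to interrupt and then reduce or discontinue for liver toxicity and diarrhea. The opening of 13.12 sends idelalisib toxicities to their own rules, and 13.1 supplies 100-mg tablets for dose reduction. The 28-day wording concerns cycle timing. What stands is an omission: no dose, no cross-reference and no stated precedence.

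On pneumonitis, the table row does not add that discontinuation is permanent. But the table uses withhold or interrupt for temporary measures, so discontinuation followed by a possible restart remains a conflict. The 100 mg daily figure for diarrhea may be a slip, since the liver and skin paragraphs say twice daily; a site cannot know that.

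None of these arguments chooses between the table and the paragraphs.

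**Conclusion.** The idelalisib rules in 13.12 contradict each other for ALT/AST, diarrhea and pneumonitis, and re-escalation to 150 mg BID appears only in the paragraphs. This needs no literal reading of any single sentence. The table differs from the paragraphs by up to 2 × ULN in the ALT/AST restart limit (1 against 3), by a factor of two in the diarrhea restart dose, and on whether idelalisib is ended at all for ALT/AST above 20 × ULN, life-threatening diarrhea and symptomatic pneumonitis. The undirected 80% criterion and the silent idelalisib restart are secondary drafting defects.

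The patient numbers above only show that the rules are likely to be used. They may be too high: the 7.2 study dosed until progression, whereas idelalisib here lasts 24 weeks. The documents give no basis for a count of patients harmed or wrongly re-exposed.

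A reader might infer damage to the response analysis or the toxicity boundary. Neither is claimed. The boundary counts patients with Grade 3 or higher non-hematological toxicity, so a patient with such an event is counted before any restart decision. Nothing in the documents allows an effect on response to be estimated.

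**What to change.** In the next amendment, change section 13.12 in this order:

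(a) State in Hepatotoxicity that ALT/AST >20 × ULN means permanent discontinuation, and use one restart threshold there and in the table. One option is <1 × ULN, or return to baseline if the eligible baseline was above ULN; a patient enrolled at 1 to 2.5 × ULN cannot reach <1 × ULN merely by returning to baseline.

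(b) In Severe Diarrhea/Colitis, restart at 100 mg BID after severe diarrhea and discontinue permanently if it is life-threatening, matching the table.

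(c) Give one pneumonitis rule in the table and the paragraph, and state once whether re-escalation to 150 mg BID is allowed.

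(d) In the Obinutuzumab delay and restart sentences, limit the 80% criterion to values that fall with toxicity, such as blood counts. For all others use Grade ≤1, or return to baseline where baseline was above Grade 1.

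(e) Only after (a) to (c), add that idelalisib restart, dose and permanent discontinuation follow the idelalisib rules. Added earlier, this sentence would give precedence to rules that still conflict. The sponsor should confirm that the lower neutrophil and platelet limits for idelalisib are intended.

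The cost is wording in the table, three idelalisib paragraphs and the Obinutuzumab text, plus the skin paragraph if re-escalation is dropped, and the usual amendment approval. No extra data or patients are needed.

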### **Progressive Multifocal Leukoencephalopathy**

A "black-box" warning for obinutuzumab states that JC viral infection (including fatal) that resulted in PML with destructive infection of oligodendrocytes of the CNS white matter have been reported in patients treated with anti-CD20 therapies, including rituximab and obinutuzumab. The diagnosis of

PML should be considered in any patient presenting with new-onset neurologic manifestations. The symptoms of PML are nonspecific and can vary depending on the affected region of the brain. Motor involvement with corticospinal tract findings, sensory involvement, cerebellar deficits, and visual field defects are common.

Some syndromes regarded as cortical (e.g., aphasia or visual-spatial disorientation) can occur. Evaluation of PML includes, but is not limited to, consultation with a neurologist, brain MRI, and lumbar puncture (cerebrospinal fluid testing for JC viral DNA).

Therapy with obinutuzumab should be withheld during the investigation of potential PML and permanently discontinued in case of confirmed PML. Discontinuation or reduction of any concomitant chemotherapy or immunosuppressive therapy should also be considered. The patient should be referred to a neurologist for the diagnosis and management of PML.

### **Management of Infusion Reactions (IRRs)**

Obinutuzumab can cause severe and life-threatening infusion reactions, mostly on Day 1 of obinutuzumab infusion. Infusion reactions can also occur with subsequent infusions. Symptoms may include hypotension, tachycardia, dyspnea, and respiratory symptoms (e.g., bronchospasm, larynx and throat irritation, wheezing, laryngeal edema). The most frequently reported symptoms include nausea, fatigue, chest discomfort, dyspnea, dizziness, vomiting, diarrhea, rash, hypertension, hypotension, flushing, headache, pyrexia, and chills. Patient premedication for IRRs is highly recommended (see *paragraph 13.4.2*)

If a patient experiences an infusion reaction of any grade during infusion, adjust the infusion as follows:

- Grade 4 (life-threatening): Stop infusion immediately and permanently discontinue obinutuzumab therapy.
- Grade 3 (severe): Interrupt infusion and manage symptoms. Upon resolution of symptoms, consider restarting obinutuzumab infusion at no more than half the previous rate (the rate being used at the time that the infusion reaction occurred) and, if patient does not experience any further infusion reaction symptoms, infusion rate escalation may resume at the increments and intervals as appropriate for the treatment cycle dose. Permanently discontinue treatment if patients experience a Grade 3 infusion-related symptom at rechallenge.
- Grade 1–2 (mild to moderate): Reduce infusion rate or interrupt infusion and treat symptoms. Upon resolution of symptoms, continue or resume infusion and, if patient does not experience any further infusion reaction symptoms, infusion rate escalation may resume at the increments and intervals as appropriate for the treatment cycle dose.

For patients with preexisting cardiac or pulmonary conditions, monitor more frequently throughout the infusion and the post-infusion period since they may be at greater risk of experiencing more severe reactions. Hypotension may occur as part of the obinutuzumab infusion reaction. Consider withholding antihypertensive treatments for 12 hours prior to, during each obinutuzumab infusion, and for the first hour after administration until blood pressure is stable. For patients at increased risk of hypertensive crisis, consider the benefits versus the risks of withholding their antihypertensive medication as is suggested here.

### **Hypersensitivity Reactions Including Serum Sickness**

Hypersensitivity reactions have been reported in patients treated with obinutuzumab. Signs of immediate-onset hypersensitivity included dyspnea, bronchospasm, hypotension, urticaria and tachycardia. Late-onset hypersensitivity diagnosed as serum sickness has also been reported, with symptoms that include chest pain, diffuse arthralgia and fever. Hypersensitivity reactions may be difficult to clinically distinguish from infusion related reactions. However, hypersensitivity very rarely occurs with the first infusion and, when observed, often occurs after previous exposure. If a hypersensitivity reaction is suspected during or after an infusion, the infusion must be stopped, and

treatment permanently discontinued. Patients with known hypersensitivity reactions to obinutuzumab, including serum sickness, must not be retreated.

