
Begin infusion at and initial rate of 50 mg/hr. If no infusion reaction occurs, increase the infusion rate in 50-mg/hr increments every 30 minutes, to a maximum of 400 mg/hr. If an infusion reaction develops, stop or slow the infusion. Administer infusion-reaction medications and supportive care in accordance with institutional protocol. Resume the infusion at a 50% reduction in rate (the rate being used at the time that the hypersensitivity or infusion-related reaction occurred) if the reaction has resolved.
	
If a patient experienced an infusion reaction or hypersensitivity during the prior infusion, use full premedication including 100 mg prednisone/prednisolone (until no further IRR occurs), begin infusion at an initial rate of 50 mg/hr, and follow instructions for first infusion. If the patient tolerated the prior infusion well (defined as an absence of Grade 2 reactions during a final infusion rate of <math>\geq 100</math> mg/hr), begin the infusion at a rate of 100 mg/hr. If no infusion reaction occurs, increase the infusion rate in 100-mg/hr increments every 30 minutes, to a maximum of 400 mg/hr. If an infusion reaction develops, stop or slow the infusion. Administer infusion-reaction medications and supportive care in accordance with institutional guidelines. If reaction has resolved, resume the infusion at a 50% reduction in rate (i.e., 50% of rate used at the time the reaction occurred)

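### The infusion table in 13.2.2 provides for re-infusing obinutuzumab after hypersensitivity at the prior infusion, while 13.12 requires permanent discontinuation and forbids retreatment

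*Combined protocol and SAP*

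**What the plan says.** Two parts of the protocol tell the site what to do with obinutuzumab after hypersensitivity.

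The administration table in 13.2.2 has one column for the first infusion and one for later infusions. The later-infusion column opens: "If a patient experienced an infusion reaction or hypersensitivity during the prior infusion, use full premedication". The premedication is to include 100 mg of prednisone or prednisolone, and the site is then told to "begin infusion at an initial rate of 50 mg/hr, and follow instructions for first infusion". In the first-infusion column, the instruction to resume at half rate once a reaction has resolved is triggered by an infusion reaction. Its parenthetical, however, defines the reference rate as "the rate being used at the time that the hypersensitivity or infusion-related reaction occurred".

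Section 13.12, under Hypersensitivity Reactions Including Serum Sickness, says: "If a hypersensitivity reaction is suspected during or after an infusion, the infusion must be stopped". The same sentence requires permanent discontinuation of treatment. The next one says: "Patients with known hypersensitivity reactions to obinutuzumab, including serum sickness, must not be retreated". Infusion reactions have their own heading in 13.12, with a graded rule that permits continuing or resuming after grade 1–2, allows a restart to be considered after grade 3, and ends treatment at grade 4.

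**The concern.** The two instructions apply to the same patient at the same decision: someone who had hypersensitivity during one obinutuzumab infusion and is due for the next. The table gives a premedication and a starting rate. Section 13.12 says there is to be no next infusion. The protocol contains no statement of precedence.

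What is at stake is the safety of an individual patient. The table is a natural reference when an infusion is being set up, and its error runs towards re-exposure. The later-infusion column is also where the rule is most needed, since 13.12 itself says that "hypersensitivity very rarely occurs with the first infusion and, when observed, often occurs after previous exposure". Under 13.3 that column covers seven further scheduled induction infusions (cycle 1 days 8 and 15, and day 1 of cycles 2 to 6: 2 + 5 = 7), and then maintenance every two months for two years in responders.

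**Working it through.** No arithmetic applies. The check is a comparison of texts.

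1. **Trigger.** The later-infusion column of 13.2.2 covers a patient who had an infusion reaction or hypersensitivity during the prior infusion. Section 13.12 covers hypersensitivity suspected during or after an infusion. The overlap is hypersensitivity during an infusion. Late-onset serum sickness falls outside the table's clause and so outside the conflict.

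2. **Action.** The table: premedicate, start at 50 mg/hr, follow the first-infusion instructions. Section 13.12: stop, discontinue permanently, do not retreat. Within the overlap these are opposites. The discontinuation rule operates on suspicion and the bar on retreatment refers to known reactions; the table's instruction runs against both.

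3. **Is hypersensitivity just another word for infusion reaction here?** The table joins the two terms with *or*, and 13.12 gives each its own heading and rule. On the face of the text they are different events.

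4. **Is it a single stray word?** It also appears in the first-infusion column, in the rate parenthetical. That column's trigger is an infusion reaction only, so it implies resumption after hypersensitivity without instructing it. The direct conflict is in the later-infusion column.

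5. **Do other rules close the gap?** In part. Section 13.12 ends treatment after a grade 4 infusion reaction. The obinutuzumab text in 13.10 ends it for hypotension needing vasopressors and for grade 3 wheezing, hypoxia or generalized urticaria. These stop many of the severest reactions whatever they are called. They do not cover suspected hypersensitivity below those thresholds.

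6. **Is there a precedence rule?** None was found in 13.2.2, 13.4.2, 13.10 or 13.12.

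**The case against.** The best reply is that the texts can be read in sequence. Section 13.12 decides whether obinutuzumab continues at all; 13.2.2 concerns preparation and administration and sets rates for an infusion that is going ahead. A site that applies 13.12 first never reaches the later-infusion column for this patient. That is a sensible reading, but the protocol does not state it, and the column names hypersensitivity as a case it is meant to handle.

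The second reply is loose drafting. The disputed sentence asks for premedication until infusion-related reactions stop, which suggests that its author had those in mind. Section 13.4.2 makes steroid premedication mandatory after an infusion-related reaction without mentioning hypersensitivity, and warns that the two may be clinically indistinguishable. This is plausible and may well explain the wording. It does not remove the word from a dosing instruction.

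A reader might also infer a second contradiction from the shared signs. Section 13.12 says: "Signs of immediate-onset hypersensitivity included dyspnea, bronchospasm, hypotension, urticaria and tachycardia". Of infusion reactions it says: "Symptoms may include hypotension, tachycardia, dyspnea, and respiratory symptoms", with bronchospasm among the examples, so four of the five signs overlap. The documents do not support that inference. The restart rules in 13.10 and 13.12 are for infusion reactions and the stop rule is for suspected hypersensitivity. Two diagnoses with shared signs and different rules are a diagnostic difficulty, which the protocol acknowledges and for which it offers a timing clue. Only the wording in the 13.2.2 table is inconsistent with 13.12.

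**Conclusion.** The protocol is wrong as written on this point: 13.2.2 and 13.12 give opposite instructions for a patient with hypersensitivity during the prior obinutuzumab infusion, and nothing says which prevails. It should be fixed, but it is not a missing safeguard. The protective rule is already stated in mandatory terms in 13.12, further stops exist in 13.10 and 13.12, and known hypersensitivity to the active substances is an exclusion criterion in 11.2. Harm requires a site to follow the table over 13.12.

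No frequency is claimed. A reader might infer one from Appendix F, which lists 9 + 9 + 2 + 2 = 22 serious immune-system reports among 3745 exposed (anaphylactic reaction, hypersensitivity, anaphylactic shock, drug hypersensitivity). Those are serious reports, whereas the part of the conflict left open by the other stop rules lies mainly in milder reactions, for which the documents give no rate. Nor do the counts show how often a site would follow the table instead of 13.12.

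A reader might also conclude that the clause cannot bite before cycle 1 day 8. That is not secure either: 13.4.2 allows an infusion to be split over two days, and the first column is labelled as day 1, so a second portion on day 2 could be taken as a subsequent infusion.

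The conclusion rests on reading the table's words at face value. If the sponsor intended only infusion-related reactions, the correction is the same.

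**What to change.** Let 13.12 govern, and say so in the table:

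- In the later-infusion column of 13.2.2, delete *or hypersensitivity* from the premedication and restart sentence.
- In the first-infusion column, delete *hypersensitivity or* from the rate parenthetical.
- Add one line to the table: *If hypersensitivity is suspected, stop the infusion and permanently discontinue obinutuzumab; do not retreat (13.12 governs).*

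The cost is protocol wording only. Sample size, error rates, visits and analyses do not change.
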